### 6.4 Concomitant Therapy

Throughout the study, Investigators may prescribe any concomitant medications or treatments deemed necessary to provide adequate supportive care except for those listed in [Section 6.8](#).

Concomitant therapies are to be collected from informed consent through EOS. Therapy name, indication, dose, unit, frequency, route, start date and stop date should be collected.

Acetaminophen (up to 2 grams per day) for analgesia, or hormone replacement therapy (eg, estrogen, thyroid) will be allowed if subject is stable on replacement therapy. Any herbal medicines, vitamins and supplements consumed by the subject within 30 days prior to receiving the first dose of AMG 529 and continuing use if considered appropriate, will be reviewed by the principal investigator and Amgen Medical Monitor. Written documentation of this review and Amgen acknowledgment are required for subject participation. Details of all concomitant medications will be recorded in the subject's source documents and on the CRF.

#### **6.5 Alcohol and Tobacco Restrictions**

Subjects must limit alcohol consumption throughout the course of the study. Alcohol is prohibited 48 hours prior to admission to the research facility (day -1) and throughout the residency period and is limited to no more than 2 drinks per day for the duration of the study (1 drink is equivalent to 12 ounces of regular beer, 8 to 9 ounces of malt liquor, 5 ounces of wine or 1.5 ounces of 80 proof distilled spirits).

Only non-nicotine or tobacco using subjects should be enrolled. Subjects should not have used any nicotine or tobacco containing products within the last 6 months prior to screening. Subjects must abstain from nicotine or tobacco containing products (including but not limited to: snuff, chewing tobacco, cigars, cigarettes, pipes, or nicotine patches) throughout the screening period and for the duration of the study.

#### **6.6 Exercise Restrictions**

Subjects are required to refrain from strenuous exercise (eg, heavy lifting, weight training, and aerobics) for 72 hours prior to each blood collection for laboratory tests for the duration of the study. Walking at a normal pace will be permitted.

#### **6.7 Product Complaints**

A product complaint is any written, electronic or oral communication that alleges deficiencies related to the identity, quality, durability, reliability, safety, effectiveness, or performance of a drug(s) or device(s) after it is released for distribution to market or clinic by either Amgen or by distributors and partners for whom Amgen manufactures the material. This includes any drug(s), device(s), or combination product(s) provisioned

and/or repackaged/modified by Amgen. Drug(s) or device(s) includes investigational product.

Any product complaint(s) associated with an investigational product(s) or non-investigational product(s) or device(s) supplied by Amgen are to be reported according to the instructions provided in the IPIM.

#### **6.8 Excluded Treatments, Medical Device Use, and/or Procedures During Study Period**

With exception to acetaminophen up to 2 g per day for analgesia and hormone replacement therapy (eg, estrogen, thyroid), use of any over-the-counter or prescription medications within the 14 days or 5 half-lives (whichever is longer) prior to dosing on day 1 and for the duration of the study is not permitted unless to treat a medical emergency. Additionally, use of any herbal medicines, vitamins or supplements known to affect lipid metabolism (eg, fish oils > 1000 mg/day, red yeast rice extract), within 30 days prior to dosing on day 1 and for the duration of the study is not permitted. It is also recommended that subjects avoid starting new or changing herbal medicines, vitamins and supplements reviewed and approved by the principal investigator and Amgen Medical Monitor during the study. Any changes regarding concomitant medications should be recorded on the subject's source documents and the CRF along with the reason for the change.

### **7. STUDY PROCEDURES**

#### **7.1 Schedule of Assessments**

Table 4. Schedule of Assessments for Cohorts 1, 2, and 6

Activity	Screening		Treatment																		EOS
Study Day	(-28 to -2)	-1	1						2		3	4	6	8	11	15	22	30			
Time (in hours) a			Pre-Dose	0	0.5	1	6	12	24	36	48	72	120	168	240	336	504	696			
Informed Consent	X																				
In-House Residency		X <	> X																		
Medical History	X	X																			
Body Weight	X																	X			
Body Mass Index	X																				
Height	X																				
Vital Signs (HR, RR, BP, TEMP)	X	X	X			X c	X	X	X		X	X	X	X	X	X	X	X			
Physical Examination	X	X																X			
12-lead ECG b	X		X			X c	X	X	X		X	X	X	X	X	X	X	X			
eGFR	X	X																X			
Clinical Chemistry d	X	X							X		X e	X	X e	X e	X	X e	X	X			
Clinical Hematology	X	X							X			X			X		X	X			
PT/INR and aPTT	X	X							X			X			X		X	X			
Urinalysis	X	X							X			X			X		X	X			
Screening Lipid Panel d	X																				
On-study Lipid Panel d			X								X		X		X		X	X			
Drug and Alcohol Screen	X	X																			
HIV, HBsAg, HBcAb, HepCAb f	X																				
Pregnancy Test (females only)	X	X																X			
Serum FSH Test (females only) g	X																				
Randomization		X																			
Study Drug Administration				X																	
Anti-Drug Antibody Sample Collection			X															X			
PK Sample Collection (SC cohorts only)			X h				X	X	X	X	X	X	X	X	X	X	X	X			
PK Sample Collection (IV cohort only)			X h		X	X	X	X	X	X	X	X	X	X	X	X	X	X			
Alkaline phosphatase isoenzymes			X								X			X				X			
Collect blood for biomarker development i			X								X			X				X			
Pharmacogenetic (optional) j			X																		
Adverse Event Recording				X <	> X																
Serious Adverse Event Recording	X <		> X																		
Concomitant Medications	X <		> X																		

a Time in hours are relative to IP administration

b A single ECG will be collected at screening. Prior to dosing day 1, 3 baseline ECGs will be collected approximately 30 minutes apart. Each baseline ECG will be in triplicate to be collected 30 seconds apart for a total of 9 ECGs. Triplicate ECGs, to be collected 30 seconds apart, will be collected at all timepoints after dosing on day 1.

c For IV cohort only

d 10 hour fasting is required at all time points

e Alkaline phosphatase only on days 3, 6, 8, and 15

f If the results show a positive HepCAb: hepatitis C virus RNA by PCR is necessary. The test must be confirmed negative at screening for the subject to be eligible for study.

g Serum FSH Test (females only) for postmenopausal status will be conducted as per [Section 7](#)

h Pre-dose PK sample will be collected approximately 1 hour prior to dosing

i Biomarker samples (plasma and serum) to be collected on days 1, 3, 8, and 30

j Pharmacogenetic sample obtained from cell pellet from the biomarker plasma sample collection at pre-dose (day 1) only

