AMG 529 displayed a concentration dependent increase in ALP in cynomolgus monkeys with a maximum increase of 400% of baseline. The cynomolgus monkey PK-PD data were analyzed using an indirect response model and this model was utilized in conjunction with the predicted human exposure to estimate the increase in ALP in humans ([Figure 2](#)). The MABEL was defined as the dose that would result in a maximum of 10-15% increase in ALP from baseline. The predicted human exposures at a starting dose of 21 mg SC are anticipated to produce minimal to no change in ALP, much lower than a 10% increase from baseline. The highest proposed dose of 700 mg SC is anticipated to achieve a 1.6-fold increase from baseline in ALP demonstrating ASGR1 target engagement by AMG 529.

**Figure 2. Predicted Alkaline Phosphatase Increase Relative to Baseline in Humans Following Single SC or IV Dose Administration of AMG 529**

In summary, the dose range of 21 to 700 mg has a first dose which is 1/10th of the MRSD, is projected to result in human exposures lower than the exposures at the NOAEL or MABEL dose, is expected to provide an ample safety margin for subjects, and results in pharmacological activity useful for dose selection in subsequent clinical studies.

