## 3. EXPERIMENTAL PLAN

### 3.1 Study Design

This is a phase 1, randomized, double-blind, placebo-controlled, ascending single-dose study in healthy subjects.

Approximately 48 subjects will enroll in 1 of 6 dose cohorts (8 per cohort). For cohorts 1, 2, 3, 4, and 5, eight (8) subjects will be randomized to receive AMG 529 or placebo SC in a 3:1 ratio at dose levels of 21, 70, 210, 420, and 700 mg, respectively.

In cohort 6, eight (8) subjects will receive AMG 529 or placebo IV in a 3:1 ratio at a dose level of 70 mg.

For all cohorts, the first 2 subjects (sentinel pair) will be randomized such that 1 subject will receive AMG 529 and 1 subject will receive placebo, and observed for at least 24 hours before the remaining subjects in the cohort are dosed, provided there are no safety or tolerability concerns as assessed by the principal investigator.

Escalation to a higher dose cohort will only proceed when the previous dose regimen has been found to be safe and reasonably tolerated based on available safety and laboratory data through study day 15 for all subjects and upon unanimous decision at the Dose Level Review Meeting (DLRM). Enrollment can be initiated in cohort 5 and cohort 6 after the dose regimen in cohort 4 has been found to be safe and well tolerated. Cohort 6 will start enrollment after the completion of cohort 5 enrollment.

The overall study design is described by a [study schema](#) at the end of the protocol synopsis section.

The study endpoints are defined in [Section 10.1.1](#).

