Escalation to a higher dose cohort will only proceed when the previous dose regimen has been found to be safe and reasonably tolerated based on available study data through study day 15 for all subjects and upon unanimous decision of the DLRM members. Available data from previous cohorts will also be considered. The next cohort will be open for enrollment immediately following the DLRM decision. Enrollment can be initiated in cohort 5 and cohort 6 after the dose regimen in cohort 4 has been found to be safe and well tolerated. Cohort 6 will start enrollment after the completion of cohort 5 enrollment.

The planned dose escalation schedule may be modified based on treatment-emergent data (safety and/or PK). Dose adjustments, if any, will be made on a treatment cohort and not on an individual basis, and will be agreed upon by Amgen in coordination with the principal investigator.

The review of available safety data and dosing change decisions will be documented in meeting minutes. Amgen will issue a written notification of the dose change decision to investigators.

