#### **6.2.1.2.2 Dose Stopping Rules**

Determination of the severity of adverse events will be as follows: grade 1 = mild (eg, asymptomatic or mild symptoms, clinical or diagnostic observations only, intervention not indicated, or does not interfere with activity); grade 2 = moderate (eg, minimal intervention indicated or interferes with activity); grade 3 = severe (eg, medically significant but not immediately life-threatening, prevents daily activity, or requires treatment); grade 4 = life-threatening (ie, refers to an event in which the subject was, in the view of the investigator, at risk of death at the time of the event); and grade 5 = fatal.

Dosing will be stopped or modified by the DLRM members if suspected adverse drug reactions and/or changes in safety data (including but not limited to vital signs, electrocardiogram (ECG), or clinical laboratory results) are observed and these changes

pose a significant health risk. The unblinded Amgen Medical Monitor will review data in an unblinded manner on an ongoing basis, and may suspend dosing and convene a DLRM at any time based on emerging safety data. In addition, dose escalation will be stopped or modified as shown in [Table 3](#).

Clinically or medically significant suspected adverse drug reactions, and serious adverse events considered to be related to study procedures will be followed until resolved or considered stable.

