### 6.3.1 Criteria for Permanent Withholding of Amgen Investigational Product and Other Protocol-required Therapies Due to Potential Hepatotoxicity

Following the single-dose administration of study drug, the subject should be followed according to the recommendations in [Appendix A](#) (Additional Safety Assessment Information) for possible drug-induced liver injury (DILI), if ALL of the criteria below are met:

- TBL > 2x upper limit of normal (ULN) or INR > 1.5
- AND increased AST or ALT from the relevant baseline value as specified below:

Baseline AST or ALT value	AST or ALT elevation
< ULN	≥ 3x ULN

- AND no other cause for the combination of the above laboratory abnormalities is immediately apparent; important alternative causes for elevated AST/ALT and/or TBL values include, but are not limited to:
  - Hepatobiliary tract disease
  - Viral hepatitis (eg, Hepatitis A/B/C/D/E, Epstein-Barr Virus, cytomegalovirus, Herpes Simplex Virus, Varicella, toxoplasmosis, and Parvovirus)
  - Right sided heart failure, hypotension or any cause of hypoxia to the liver causing ischemia.
  - Exposure to hepatotoxic agents/drugs or hepatotoxins, including herbal and dietary supplements, plants and mushrooms
  - Heritable disorders causing impaired glucuronidation (eg, Gilbert's Syndrome, Crigler-Najjar syndrome) and drugs that inhibit bilirubin glucuronidation (eg, indinavir, atazanavir)
  - Alpha-one antitrypsin deficiency
  - Alcoholic hepatitis
  - Autoimmune hepatitis
  - Wilson's disease and hemochromatosis
  - Nonalcoholic Fatty Liver Disease including Steatohepatitis (NASH)
  - Non-hepatic causes (eg, rhabdomyolysis, hemolysis)

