**Table 5. Schedule of Assessments for Cohorts 3, 4, and 5**

Activity	Screening		Treatment																EOS
	Study Day		1				2		3	4	6	8	11	15	22	30	43	57	
Time (in hours) a			Pre-Dose	0	6	12	24	36	48	72	120	168	240	336	504	696	1008	1344	
Informed Consent	X																		
In-House Residency		X <	> X																
Medical History	X	X																	
Body Weight	X																		X
Body Mass Index	X																		
Height	X																		
Vital Signs (HR, RR, BP, TEMP)	X	X	X		X	X	X		X	X	X	X	X	X	X	X	X	X	X
Physical Examination	X	X																	X
12-lead ECG b	X		X		X	X	X		X	X	X	X	X	X	X	X	X	X	X
eGFR	X	X																	X
Clinical Chemistry c	X	X					X		X d	X	X d	X d	X	X d	X	X	X d	X	X
Clinical Hematology	X	X					X			X						X	X		X
PT/INR and aPTT	X	X					X			X					X	X	X		X
Urinalysis	X	X					X			X				X		X	X		X
Screening Lipid Panel c	X																		
On-study Lipid Panel c			X						X		X		X		X	X			X
Drug and Alcohol Screen	X	X																	
HIV, HBsAg, HBcAb, HepCAb e	X																		
Pregnancy Test (females only)	X	X																	X
Serum FSH Test (females only) f	X																		
Randomization		X																	
Study Drug Administration				X															
Anti-Drug Antibody Sample Collection			X																X
PK Sample Collection			X g		X	X	X	X	X	X	X	X	X	X	X	X	X	X	X
Alkaline phosphatase isoenzymes			X						X			X					X		
Collect blood for biomarker development h			X						X			X					X		
Pharmacogenetic (optional) i			X																
Adverse Event Recording				X <	> X														
Serious Adverse Event Recording	X <																		> X
Concomitant Medications	X <																		> X

a Time in hours are relative to IP administration

b A single ECG will be collected at screening. Prior to dosing day 1, 3 baseline ECGs will be collected approximately 30 minutes apart. Each baseline ECG will be in triplicate to be collected 30 seconds apart for a total of 9 ECGs. Triplicate ECGs, to be collected 30 seconds apart, will be collected at all timepoints after dosing on day 1.

c 10 hour fasting is required at all time points

d Alkaline phosphatase only on days 3, 6, 8, 15, and 43

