The investigator is responsible for reviewing laboratory test results and determining whether an abnormal value in an individual study subject represents a clinically significant change from the subject’s baseline values. In general, abnormal laboratory findings without clinical significance (based on the Investigator’s judgment) are not to be recorded as adverse events. However, laboratory value changes that require treatment or adjustment in current therapy are considered adverse events. Where applicable, clinical sequelae (not the laboratory abnormality) are to be recorded as the adverse event.

The investigator is expected to follow reported adverse events until stabilization or reversibility.

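### Cohorts 1 to 4: day 15 chemistry at the escalation cut is ALP only, so the last scheduled AST, ALT, GGT and bilirubin before the decision are from day 11 (optional, inexpensive improvement)

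*Protocol*

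**What the plan says.** Protocol 3.1 makes escalation conditional on the previous dose being judged safe and reasonably tolerated "based on available safety and laboratory data through study day 15 for all subjects", with a unanimous decision at the Dose Level Review Meeting (DLRM). Section 6.2.1.2.1 repeats the day 15 cut and adds "Available data from previous cohorts will also be considered". Cohort 4 is the gate for both cohort 5 and cohort 6, so the cut governs four decisions: those after cohorts 1, 2, 3 and 4.

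The schedules in Protocol 7.1 limit some chemistry draws to one analyte. Footnote e of Table 4 (cohorts 1, 2 and 6) reads "Alkaline phosphatase only on days 3, 6, 8, and 15". Footnote d of Table 5 (cohorts 3, 4 and 5) reads "Alkaline phosphatase only on days 3, 6, 8, 15, and 43". Table 7 places AST, ALT, GGT, and total and direct bilirubin in the clinical chemistry panel, so on those days they are not scheduled.

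Section 2.3 expects ALP, and possibly GGT, to rise because the drug slows their clearance. It says that such rises do not signal liver toxicity, and it expects the remaining liver tests to stay free of clinically relevant increases.

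**The concern.** The only liver analyte scheduled on the day of the cut is the one least able to show liver injury with this drug. An ALP rise is the intended pharmacology. What would separate that from injury is AST, ALT and bilirubin measured beside it, and these were last scheduled on day 11.

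At stake is a transaminase or bilirubin rise without symptoms that begins between day 11 and day 15. No scheduled result would show it at the meeting, and the next cohort opens immediately after the decision.

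**Working it through.** **Which days carry a full panel.** The schedule's hours convert to study days as hours/24 + 1: 240 h is day 11, 336 h is day 15 and 504 h is day 22.

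- Table 4 chemistry: screening, day -1, and days 2, 3 (ALP), 4, 6 (ALP), 8 (ALP), 11, 15 (ALP), 22 and 30. That is 11 collections. 11 × 8.5 mL = 93.5 mL, the figure in Table 10.
- Table 5 chemistry: the same 11 plus days 43 (ALP) and 57, which is 13. 13 × 8.5 mL = 110.5 mL, the figure in Table 11.

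Both counts match the plan's own. Both footnotes name day 15 and neither names day 11, so the reading does not depend on how the table columns line up. The ALP-only days are counted at the full 8.5 mL. Post-dose full panels inside the cut are therefore days 2, 4 and 11.

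**Distance from the last full panel to the cut.** Section 7.2 allows ±1 day on days 8 to 22. The cut is fixed at study day 15; only the draw moves.

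- Nominal: 15 − 11 = 4 days.
- Day 11 draw taken on day 12 or day 10: 15 − 12 = 3 to 15 − 10 = 5 days.

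**Interval between scheduled hepatic panels around the decision.**

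| Schedule | Longest interval | Nominal | With windows |
|---|---|---|---|
| As planned | day 11 to 22 | 11 days | 21 − 12 = 9 to 23 − 10 = 13 |
| With day 15 panel | day 15 to 22 | 7 days | 21 − 16 = 5 to 23 − 14 = 9 |

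**Who is affected.** Subjects dosed last, when the meeting is held as early as possible. A subject dosed at least 22 − 15 = 7 days before the last one could already have a day 22 panel. The required sentinel lead is only 24 hours.

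**Expected risk.** Table 1 gives predicted AUC margins to the monkey no-adverse-effect level of 113000, 33200, 10300 and 4460 for the four doses. The smallest reproduces: 11200 × 1000 / 2510 = 4462, given as 4460.

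**Size of the change.** 4 cohorts × 8 subjects = 32 panels (24 on AMG 529, 8 on placebo). 32 × 5 analytes = 160 results.

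**The case against.** The case against acting is substantial.

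- **The prior evidence is reassuring.** Section 2.2.3 reports no ALT, AST or total bilirubin increases in monkeys up to the no-adverse-effect level. Section 2.3 reports no association of the human loss-of-function variant with ALT, AST or bilirubin. The predicted margins are very large.
- **There are several safeguards.** Full panels fall on days 2, 4 and 11. Extra tests are allowed when clinically indicated (7.2.5.14). The investigator is responsible for "determining whether an abnormal value in an individual study subject represents a clinically significant change". The unblinded medical monitor "may suspend dosing and convene a DLRM at any time based on emerging safety data". Each cohort starts with a sentinel pair. At 21 mg the predicted exposure is "anticipated to produce minimal to no change in ALP, much lower than a 10% increase from baseline", so a marked ALP rise there would be unexpected and could prompt more tests.
- **The schedule is coherent.** ALP is a secondary pharmacodynamic endpoint, and the ALP-only days fit added sampling for it. In Table 4, full chemistry, hematology, coagulation and urinalysis fall together on days 2, 4, 11 and 22. A 7-day gap between hepatic panels (day 4 to 11) is already accepted, and the documents set no maximum.

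All of this stands, and it lowers the severity. It does not supply a result: the investigator and the monitor can act only on values that were measured, a silent rise gives no clinical indication for extra tests, and earlier cohorts had lower doses. The argument rests on where the gap falls and how little it costs to close, not on a rule about interval length.

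A reader might infer more than the documents support, in four ways.

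- *That the protocol contradicts itself.* It asks only for available data through day 15, and ALP-only data satisfy that.
- *That an escalation criterion cannot be applied.* The liver-injury criterion in 6.3.1 combines AST or ALT with "TBL > 2x upper limit of normal (ULN) or INR > 1.5". It governs follow-up and reporting for an individual and is not among the cohort stopping rules in Table 3. Its bearing on escalation is indirect.
- *That the gap is 2 to 6 days.* That is the possible spacing between the day 11 and day 15 visits when both move. The distance to the fixed cut is 3 to 5 days.
- *That liver injury is likely to be missed.* The documents give no rate or timing for transaminase changes in humans.

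**Conclusion.** The point holds as an optional improvement of low severity for cohorts 1 to 4. At the earliest escalation decision, scheduled AST, ALT, GGT and bilirubin reach only to day 11, and the next are due on day 22.

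The figures describe schedule coverage only; no probability of a missed event is claimed. They assume visits within the stated windows, no unscheduled liver tests, and a meeting held as soon as the last subject reaches day 15. No claim is made about cohorts 5 and 6, after which no planned escalation follows.

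**What to change.** In cohorts 1 to 4, run AST, ALT, GGT, and total and direct bilirubin alongside ALP on the day 15 chemistry sample. Require those results at the DLRM even when the draw falls on day 16, which the window allows; otherwise a compliant draw could miss the cut. Days 3, 6, 8 and 43, and day 15 in cohorts 5 and 6, can stay ALP only.

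The cost is the 32 panels, investigator review and sign-off of the results (7.2.5.14), and an amendment of both schedule tables with IRB approval (12.1). The day 15 visit, the fasting draw and the 8.5 mL are already planned, so none of these increases. INR would remain unscheduled on day 15, because it needs the separate 2.7 mL coagulation sample; only the AST or ALT plus bilirubin combination becomes readable that day.

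If the schedule is left as it is, one sentence in 6.2.1.2.1 should say that the scheduled DLRM basis is full chemistry through day 11 and ALP through day 15.
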